9.5. EFFICACY AND SAFETY VARIABLES

9.5.1. Efficacy and Safety Measurements Assessed and Flow Chart

The primary objective of this study is to evaluate the ocular hypotensive efficacy of 2 concentrations of VVN539 in subjects with ocular hypertension (OHT) or primary open angle glaucoma (POAG). The secondary objective is to evaluate the ocular and systemic safety of the 2 concentrations in this subject population.

Figure 1 summarizes the design of the study.

[figure not shown]

Figure 1: Study Schematic

9.5.1.1. Visit and Procedure Schedule

See Table 1 in Appendix I for a complete visit and procedure schedule.

9.5.1.2. Demographics and Baseline Characteristics

9.5.1.2.1. Demographics and Disease Characteristics

Demographic characteristics such as age (years), sex, race, and ethnicity and the normality of nerve fiber layer thickness will be collected at Visit 1. Baseline diurnal intraocular pressure (IOP) will be collected at Visit 2.

9.5.1.2.2. Medical and Surgical History

Ocular and non-ocular medical history will be collected at Visits 1 and 2.

9.5.1.2.3. Prior and Concomitant Medications

All medications that the subject has taken 2 months prior to Visit 1 and/or is taking through Visit 6 (or discontinuation from the study) will be recorded in the subject chart and the eCRF. The generic name of the drug, dose, route of administration, duration of treatment (including start and stop dates), frequency, indication and whether or not the medication was taken due to an AE will be recorded for each medication.

For this protocol, a prescription medication is defined as a medication that can be prescribed only by a properly authorized/licensed clinician. Medications to be reported in the case report form are concomitant prescription medications, over-the-counter medications and supplements.

9.5.1.2.4. Prohibited and Rescue Medications

Table 2 of the protocol lists medications and procedures that are exclusionary for the study and/or are prohibited during study participation.

Any subject who has an elevated IOP that the PI considers unsafe for the subject may be rescued and placed on appropriate alternate therapy. The choice of rescue medication is at the Investigator's discretion. Rescue medication should be entered into the eCRF with annotation indicating that the medication was used for rescue.

Rescued subjects will be considered as treatment failures, and the need for rescue therapy will not be considered an adverse event (AE). Rescued subjects will stop the investigational product and should not be withdrawn from the study.

The following guidance is provided to Investigators for rescue and the decision to rescue is at the discretion of the investigator's judgement:

- Ocular hypotensive medication (other than IP) is prohibited during study participation unless the subject is rescued.
- If the subject's IOP is > 36 mmHg, the Investigator may recheck the IOP within 3 day of the visit and rescue medication may be considered if the IOP remains elevated.
- Rescued subjects should discontinue the investigational product.
- Rescued subjects should continue in the study for safety follow-up after receiving the rescue medication.

9.5.1.3. Efficacy Assessments

9.5.1.3.1. Primary Efficacy Assessment(s)

The study has a single primary assessment that compares the mean IOP in the study eye at each diurnal time point (8AM, 10AM, and 4PM) at Visits 4, 5, and 6 for two doses of VVN539 compared to vehicle.

9.5.1.3.2. Secondary Efficacy Assessments

Secondary efficacy assessments will examine:

- Change from baseline (Visit 2) in IOP at each diurnal time point to Visits 4, 5, and 6;
- Change from baseline (Visit 2) in diurnal IOP to Visits 4, 5, and 6. Diurnal IOP is the average of 8AM, 10AM, and 4PM measurements at a given visit.

9.5.1.3.3. Description of Efficacy Assessments

IOP measurements will be performed utilizing a Goldmann applanation tonometer affixed to a slit lamp according to the Investigator's standard procedure (two-person reading method). Measurements will be taken with the subject seated. All pressure will be recorded in mmHg. Two consecutive measurements are taken in each eye and recorded as the mean of the two measurements. If the two measurements differ by >1.0 mmHg, a third measurement is performed, and the median is recorded.

At Visit 1, IOP will be measured once during screening visit.

At Visit 3, IOP will be measured once at 8:00AM (± 30 minutes) prior to the first q.d. AM dosing.

At Visits 2, 4, 5, and 6 diurnal IOP will be measured:

- At 8:00AM (± 30 minutes), 10:00AM (± 30 minutes) and 4:00PM (± 30 minutes)
- At Visits 4 and 6, the 8:00AM measurement will be taken prior to the AM dosing.

9.5.1.4. Safety Assessments

The safety of VVN539 ophthalmic solution will be evaluated using the following assessments.

1. Adverse event (AE) monitoring
2. Best corrected visual acuity (BCVA)
3. Slit-lamp biomicroscopy
4. Central corneal thickness
5. Dilated ophthalmoscopy
6. Heart rate and blood pressure
7. Clinical laboratory tests (blood chemistry, hematology)

9.5.1.4.1. Adverse Events

AEs will be monitored throughout the study. Subjects will be encouraged to report any adverse findings during the study whether or not they are related to IP. These can be collected either in an unsolicited fashion without any prompting or in response to a general question such as: "Have you noticed anything different since you started the study; began the IP, etc?"

All AEs will be captured on the appropriate eCRF. Information to be collected at minimum includes event description, onset, assessment of severity, relationship to IP, and outcome.

The Investigator will record all AEs with start dates occurring any time after informed consent is obtained until 7 (for nonserious AEs) or 30 days (for SAEs) after the last day of study participation. At each study visit, the Investigator will inquire about the occurrence of AE/SAEs since the last visit. Events will be followed for outcome information until resolution or stabilization.

Any medical condition that is present at the time that the subject is screened will be considered as baseline and not reported as an AE. However, if the study subject's condition deteriorates at any time during the study, it will be recorded as an AE.

An AE is any untoward medical occurrence in a patient or clinical study subject, temporally associated with the use of study intervention, whether or not considered related to the study intervention. An AE can therefore be any unfavorable and unintended sign (including an abnormal laboratory finding), symptom, or disease (new or exacerbated) temporally associated with the use of study intervention.

An AE or suspected adverse reaction is considered "serious" if, in the view of either the Investigator or Sponsor, it results in any of the following outcomes:

- Death,
- A life-threatening AE,
- Inpatient hospitalization or prolongation of existing hospitalization,
- A persistent or significant incapacity or substantial disruption of the ability to conduct normal life functions, or
- A congenital anomaly or birth defect.

Important medical events that may not result in death, be life-threatening, or require hospitalization may be considered serious when, based upon appropriate medical judgment, they may jeopardize the subject and may require medical or surgical intervention to prevent one of the outcomes listed in this definition.

The severity of all AEs will be assessed by the Investigator and graded as follows:

- **Mild:** requires minimal or no treatment and do not interfere with the subject's daily activities;
- **Moderate:** results in a low level of inconvenience or concern and may cause some interference with functioning;
- **Severe:** interrupts a subject's usual daily activity and may require systemic drug therapy or other treatment. Severe events are usually potentially life-threatening or incapacitating. The term "severe" does not necessarily equate to "serious".

All AEs must have their relationship to study intervention assessed by the Investigator who examines and evaluates the subject based on temporal relationship and his/her clinical judgment. The degree of certainty about causality will be graded using the categories below. In a clinical study, the IP must always be suspect.

- **Unrelated:** no reasonable possibility that the administration of the IP caused the event, no temporal relationship between the IP and event onset, or an alternate etiology has been established.

- **Related:** is known to occur with the IP, is a reasonable possibility that the IP caused the AE, or there is a temporal relationship between the IP and event. Reasonable possibility means that there is evidence to suggest a causal relationship between the IP and the AE.

9.5.1.4.2. Best Corrected Visual Acuity (BCVA)

The BCVA will be measured on both eyes in LogMAR at every study visit using Early Treatment Diabetic Retinopathy Study (ETDRS) charts. LogMAR is calculated as Baseline value + (n × 0.02); where the baseline value is the LogMAR number of the last line read (at least one letter read correctly in this line), “n” is the total number of letters missed up to and including the last line read, and “0.02” is the value for each letter.

9.5.1.4.3. Slit-Lamp Biomicroscopy

The slit-lamp biomicroscopy exam will be performed to examine eye structures for each eye at each study visit.

This procedure will be performed in the same manner for all subjects observed at the Investigator's site. The site will record all ABNORMAL findings in the source document and the Investigator will evaluate the ABNORMAL findings as Not Clinically Significant (NCS) or Clinically Significant (CS). CS and NCS ABNORMAL findings will be recorded in the source documentation. However, only ABNORMAL CS descriptions from Visits 3-6 will be captured in the eCRF as AE.

Findings for the anterior chamber (cells and flare), eyelid (hyperemia and edema), conjunctiva (hyperemia, edema (chemosis), discharge/exudate), cornea (edema), iris color, pupil, lashes, and lens will be collected.

9.5.1.4.4. Central Corneal Thickness

Corneal thickness evaluation (in microns) will be performed using a calibrated ultrasonic or optical pachymeter, provided that the same method is used for all measurements. Measurements will be taken in the central cornea after instilling topical anesthetic. A total of three readings will be obtained for each eye. Care should be taken to place the probe perpendicular to the corneal surface and to not compress the cornea.

Pachymetry is performed at Visit 1 and Visit 6.

- At Visit 1, pachymetry within 3 months of the visit is acceptable.
- At Visit 6, Pachymetry is to be performed after the last IOP measurement.

9.5.1.4.5. Dilated Ophthalmoscopy

Dilated ophthalmoscopy will be performed at Visit 1 and Visit 6 and will include assessment of the retina for any abnormal findings and optic nerve head for pallor and cupping (cup to disc ratio). The status of the vitreous (including haze), retina (including vessels), macula, optic nerve will be determined as Normal or Abnormal. The cup-to-disc ratio will be recorded with two decimal points (e.g., 0.80).

9.5.1.4.6. Heart Rate and Blood Pressure

Heart rate and blood pressure will be measured at each study visit.

Heart rate will be measured after the subject has been seated for at least 5 minutes. The pulse rate will be measured over a 30-second period by palpitation at the wrist, and multiplied by 2. An electronic device may be used instead. The method of measurement (manual or electronic) must be documented in the subject records. Repeat measurements should be taken for out-of-range values. Confirmed heart rate readings outside the normal range must be evaluated by the Investigator for clinical significance.

Blood pressure will be measured after heart rate (while the subject is in a resting state). A sphygmomanometer with appropriate size cuff with a stethoscope will be used. A digital device may be used instead. All measurements will be obtained from the same arm using the same cuff size for all study visits. Repeat measurements should be taken for significantly high or low measurements. Confirmed BP readings outside the normal range must be evaluated by the Investigator for clinical significance.

9.5.1.4.7. Clinical Laboratory Tests (Blood Chemistry, Hematology)

Approximately 10 mL of blood will be obtained at Visit 1 and Visit 6. Fasting will not be required, therefore specific values may be out of the typical fasting range.

Abnormal laboratory values noted as clinically significant at Visit 6 that are changes from the Screening values are documented as AEs and is to be followed-up as appropriate.

The following serum chemistry and hematology parameters will be measured:

Chemistry	Hematology
Alanine aminotransferase (ALT)	Absolute/percent basophil count
Albumin	Absolute/percent eosinophil count
Alkaline phosphatase (ALP)	Absolute/percent lymphocyte count
Aspartate aminotransferase (AST)	Absolute/percent monocyte count
Bilirubin (total, direct, indirect)	Absolute/percent neutrophil count
BUN	Differential WBC
Calcium	Hematocrit (Hct)
Cholesterol (total, High-Density	Hemoglobin (Hgb)
Lipoprotein (HDL) and Low-Density	Mean corpuscular hemoglobin (MCH)
Lipoprotein (LDL))	Mean corpuscular hemoglobin conc. (MCHC)
Carbon dioxide	Mean corpuscular volume (MCV)
Chloride	Platelet count
Creatinine, serum	Red blood cells (RBC)
Glucose	White blood cells (WBC)
Lactate dehydrogenase (LDH)	
Potassium	

Sodium
Total protein
Triglycerides

9.5.2. Appropriateness of Measurements

All assessments used in this study are widely used and generally recognized as reliable, accurate, and relevant.

9.5.3. Primary Efficacy Variable(s)

The primary efficacy endpoint for this study is to compare mean IOP at each diurnal time point (8AM, 10AM, and 4PM) at Visit 4 (Day 7), Visit 5 (Day 14), and Visit 6 (Day 21) for two doses of VVN539 compared to vehicle using data from the study eye.

To claim superiority, the two-sided 95% confidence interval estimates of the treatment differences in mean IOP between VVN539 and vehicle must exclude zero for all 9 time points.

9.5.4. Drug Concentration Measurements

No drug concentration measurements will be made for this study.

9.6. DATA QUALITY ASSURANCE

Quality control (QC) procedures will be implemented beginning with the data entry system and data QC checks that will be run on the database will be generated. Any missing data or data anomalies will be communicated to the site(s) for clarification/resolution.

Following written Standard Operating Procedures (SOPs), the monitors will verify that the clinical trial is conducted and data are generated and biological specimens are collected, documented (recorded), and reported in compliance with the protocol, International Council for Harmonisation (ICH) Good Clinical Practice (GCP), and applicable regulatory requirements (e.g., Good Laboratory Practice [GLP], Good Manufacturing Practices [GMP]).

The investigational site will provide direct access to all trial related sites, source data/documents, and reports for the purpose of monitoring and auditing by the Sponsor, and inspection by local and regulatory authorities.

9.6.1. Training and Education of Investigators and Study Site Personnel

An Investigator Meeting will be held before study initiation and attended by the Investigators and/or Sub-Investigators from each study site, study coordinators from each study site, if possible, and personnel from the sponsor and the Contract Research Organization (CRO), Lexitas Pharma Services, Inc. (hereafter referred to as Lexitas). The purpose of this meeting is to ensure the Investigators and study coordinators are trained and instructed on the proper conduct of the clinical trial and ensure that all participants are aware of their obligations set out by the protocol, ICH guidelines, GCP guidelines, and other applicable regulatory requirements.

9.6.2. Monitoring of Study Sites

Lexitas Pharma Services, Inc. will conduct the clinical monitoring for this study. A clinical Monitoring Plan is to be used, which will describe in detail who will conduct the monitoring, at what frequency monitoring will be done, at what level of detail monitoring will be performed and the distribution of monitoring reports.

9.6.3. Data Entry and Verification of Database Used for Analysis and Reporting

Data collection is the responsibility of the clinical trial staff at the site under the supervision of the site's Investigator. The Investigator is responsible for ensuring the accuracy, completeness, legibility, and timeliness of the data reported.

All source documents should be completed in a neat, legible manner to insure accurate interpretation of data. Data recorded in the eCRF derived from source documents should be consistent with the data recorded on the source documents.

Clinical data (including AEs, concomitant medications, and expected adverse reactions data) will be entered into IBM Clinical Development, a 21 CFR Part 11-compliant data capture system provided by Lexitas Pharma Services, Inc. The data system includes password protection and

internal quality checks, such as automatic range checks, to identify data that appear inconsistent, incomplete, or inaccurate. Clinical data will be entered directly from the source documents.

9.6.4. Clinical Study Report

The final clinical study report will be reviewed, audited, and approved by medical, clinical, statistical, and regulatory staff from the sponsor, and key study contributors from Lexitas.

9.6.5. Inter-Laboratory Standardization Methods

Not applicable. A single, qualified, and certified central clinical laboratory will be used to analyze and report clinical laboratory data.

9.7. STATISTICAL METHODS PLANNED IN THE PROTOCOL AND DETERMINATION OF SAMPLE SIZE

This section of the analysis plan describes the analyses explicitly mentioned in the protocol as well as additional analyses not explicitly mentioned in the protocol but planned prior to breaking the treatment mask. Section 9.8 describes any changes to analyses that were explicitly mentioned in the protocol or statistical analysis plan.

9.7.1. Statistical and Analytical Plans

General Conventions

Summary statistics for the data collected during this study will be presented to give a general description of the patients studied. Data from all sites will be combined in the computation of these descriptive summaries. Categorical variables will be summarized by the frequency and percentage of patients in each category. Continuous variables will be summarized using N, mean, standard deviation (SD), median, minimum, and maximum values.

Number of subjects, minimums, and maximums will be calculated to the same number of decimal places as the source data. Means, medians, standard deviations, standard errors, and quartiles will be calculated to one more decimal place than the source data. Percentages will be calculated to the nearest one decimal place and will use the number of non-missing responses as the denominator, unless otherwise noted. Zero count cells will be displayed as "0" with percentage of (0%). Unless otherwise noted, summaries will be performed by the treatment group and presented in the order of: VVN539, 0.04%; VVN539, 0.02%; Vehicle.

Statistical tests will be presented as two-sided p-values rounded to four decimal places; p-values less than 0.0001 will be presented as '<0.0001' and p-values = 1 will be presented as '>0.9999' in all tables. Unless otherwise indicated, statistical testing will be carried out at the $\alpha = 0.05$ significance level.

Baseline values will be defined as the last scheduled or unscheduled measurement prior through Visit 2. Ocular measurements will use the most recent measurement for each eye.

Numeric laboratory data may be recorded at limits of detection (with a '<' or '>' sign, i.e. <0.1 or >0.1). To summarize the data, the original value will be converted to one unit less or more at the level of measured precision (e.g. 0.4 in the case of <0.5 and to 0.6 in the case of >0.5). The actual values will be presented in the data listings.

All data collected in this study will be presented in individual patient data listings for all patients.

Computations for all results will be performed using SAS (Version 9.4, SAS/STAT 15.2) computer software package (SAS Institute, Inc, 2013, 2020), unless otherwise specified.

Strata and Covariates

For analysis of efficacy endpoints, analysis of covariance (ANCOVA) or longitudinal models will model the observed value or change from baseline of each endpoint as the dependent variable with the baseline measurement of the corresponding endpoint as a covariate and treatment group as a main effect. Longitudinal models will include a covariate for visit as well as an interaction term for visit and treatment.

Subgroups

Not applicable.

Multiplicity

Time-matched longitudinal models adjusting for baseline and including a random effect for center will be used to test time-specific superiority comparisons as well as the overall superiority hypothesis using 95% confidence intervals. To claim study success for the primary endpoint based on the model, the two-sided 95% confidence interval estimates of the treatment differences in mean IOP between VVN539 and vehicle must exclude zero for all 9 time points (8AM, 10AM, and 4PM at Visits 4, 5, and 6). No adjustment to the individual confidence intervals is required since all criteria need to be met to claim superiority.

Comparisons will be made first between VVN539, 0.04% versus vehicle. If the treatment differences for all 9 time points are statistically significant, testing will proceed to VVN539, 0.02% versus vehicle.

Missing Data and Outliers

Every attempt will be made to capture all study data. The primary analysis will be analyzed using observed data assuming missing at random (MAR) using a longitudinal model (mixed model repeated measures, MMRM). Sensitivity analyses of the primary endpoint will be performed utilizing time-matched last observation carried forward (LOCF) of the last available IOP measurement.

Safety analyses will use observed data only.

Visit Windows

The nominal visits listed in the CRF will be used in the summaries. In general, unscheduled visits will not be summarized in tables unless otherwise noted.

Missing Dates

Missing dates that occur for prior or concomitant medications or adverse events will be queried for a date. If no date is obtained, the following imputation rules will apply:

- For start dates, if the given year (or year-month) is the same as study drug administration, the start date will be imputed as study drug administration date; otherwise, missing month-day (or day) will be imputed as '01-01' (or '01').

- For stop dates, missing months will be imputed as '12' and missing days will be imputed as the last day of the month. If this creates a date after discontinuation/completion, the date of discontinuation/completion will be used.

Imputed dates will only be used to classify events or medications, such as occurring before or after the start of treatment. Imputed dates will only be used in tables. Listings will display the collected date data.

Interim Analysis

There is no unmasked efficacy or futility interim analysis for this study.

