7.1.3 Visit 3 (Day 1)

The following procedures will be performed at Visit 3 (Day 1). Ophthalmic procedures should be performed in the order suggested below:

- BCVA
- Biomicroscopy
- IOP
 - Measured using Goldmann applanation tonometer and a two-person reading method.
 - Reading at:
 - 8:00AM (± 30 mins)
 - Measure twice in each eye; if results differ by >1 mm Hg, a third measurement will be obtained. The mean will be taken if two measurements are used, for 3 measurements record the median.
- Administer first dose of study drug in clinic after IOP is taken.
- Dispense study drug
- Instruct subject to dose daily in the morning (suggested timing between 7:00AM and 9:00AM).
- Blood pressure & heart rate
- Update concomitant medications, as needed
- Adverse event assessment

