12.3 Appendix 3: Visual Acuity

Distance visual acuity (VA) will be assessed as outlined in [Appendix 1](#) using ETDRS visual acuity charts either retro-illuminated or frontally illuminated (60-watt bulb or well-lit room, respectively). It is recommended that the ETDRS Chart 1 be used for testing the right eye and the Chart 2 be used for testing the left eye.

BCVA testing should precede slit lamp examination, intraocular pressure measurement, the administration of topical anesthetic agents or any examination requiring contact with the eye.

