12.5 Appendix 5: Intraocular Pressure

IOP measurement should be conducted after the biomicroscopy exam is completed and prior to pupil dilation, as applicable.

IOP measurements will be performed utilizing a Goldmann applanation tonometer affixed to a slit lamp according to the Investigator's standard procedure (two-person reading method). Measurements will be taken with the subject seated. The subject and slit lamp should be adjusted so that the subject's head is firmly positioned on the chin rest and against the forehead rest without leaning forward or straining. All pressure will be recorded in mmHg. Two consecutive measurements are taken in each eye and recorded as the mean of the two measurements. If the two measurements differ by >1.0 mmHg, a third measurement is performed, and the median is recorded.

At Visit 1, IOP will be measured once during screening visit.

At Visit 3, IOP will be measured once at 8:00AM (± 30 minutes) prior to the first q.d. AM dosing.

At Visits 2, 4, 5, and 6 diurnal IOP will be measured:

- At 8:00AM (± 30 minutes), 10:00AM (± 30 minutes) and 4:00PM (± 30 minutes)
- At Visits 4 and 6, the 8:00AM measurement will be taken prior to the AM dosing.

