APPENDIX I: SCHEDULE OF ASSESSMENTS

Table 1: Schedule of Assessments

Study Period	Screening	Washout ¹	Baseline	Treatment Period				End of Treatment
				2	3	4	5	
Visit No.	1		2	Day 0	Day 1	Day 7 (+2)	Day 14 (+2)	6
Visit Window	Day-35 to -1							Day 21 (+2)
Informed consent ²	X							
Ocular and medical history	X		X					
Demographics	X							
Inclusion/Exclusion criteria	X		X					
BCVA	X			X	X	X	X	X
Biomicroscopy ³	X			X	X	X	X	X
IOP	X				X ⁴			
Diurnal IOP ⁵			X			X	X	X
Cup-to-disc ratio	X							X
Dilated ophthalmoscopy	X							X ⁶
Pachymetry ⁷	X							X
Gonioscopy ⁸	X							

¹ Washout period: Prostaglandins, β -adrenoceptor antagonists, kinase inhibitors (4 weeks), adrenergic agonists (2 weeks), muscarinic agonists and carbonic anhydrase inhibitors (5 days)

² Informed consent will be obtained prior to the conduct of any study specified or associated procedures or evaluations.

³ Biomicroscopy of anterior segment includes corneal epithelium, bulbar and lower conjunctiva, and lens.

⁴ Measured at 8:00AM

⁵ Measured at 8:00AM, 10:00AM and 4:00PM

⁶ After the last IOP measurement

⁷ Central corneal thickness will be measured at entry for IOP interpretation. Pachymetry performed within 3 months of screening is acceptable. Ultrasound and optical pachymetry is permissible provided that the same methodology is used at Visits 1 and 6.

⁸ Gonioscopy performed within 3 months of Visit 1 is acceptable.

Study Period	Screening	Washout ¹	Baseline	Treatment Period			End of Treatment
Visit No.	1		2	3	4	5	6
Visit Window	Day-35 to -1		Day 0	Day 1	Day 7 (+2)	Day 14 (+2)	Day 21 (+2)
Visual field ⁹	X						
Optical Coherence Tomography	X ¹⁰						
Blood chemistry, hematology	X						X
BP, HR	X		X	X	X	X	X
Pregnancy test ¹¹	X		X				X
Randomization			X				
Study drug administration in clinic				X ¹²	X ¹³		X ¹³
Dispense investigational product				X	X	X	
Collect study drug					X	X	X
Prior/Concomitant medications	X		X	X	X	X	X
Adverse event assessment			X	X	X	X	X

Abbreviation key: BCVA=best corrected visual acuity; BP=blood pressure; HR=heart rate; IOP=intraocular pressure

⁹ Visual field within 3 months of Visit 1 is acceptable, provided that it is reliable and meets the requirement for automated threshold visual field (e.g., 30-2 or 24-2 Humphrey). Unreliable entry fields must be repeated prior to study drug dispensation.

¹⁰ Optical Coherence Tomography within 3 months of Visit 1 is acceptable.

¹¹ Women of childbearing potential only

¹² After 8:00AM IOP measurement

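### The Visit 3 visual acuity and slit-lamp exams are planned before the first dose, but the SAP reports them as post-baseline, and a finding dated to that slit-lamp exam can count as treatment-emergent

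*SAP*

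**What the plan says.** SAP 9.7.1 (General Conventions) sets one baseline rule: "Baseline values will be defined as the last scheduled or unscheduled measurement prior through Visit 2". Visit 2 is Day 0. Under Protocol 3.1 and 5.1.2, treatment begins at Visit 3, the next day.

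Protocol 7.1.3 lists the Visit 3 eye procedures as BCVA, biomicroscopy and IOP, followed by "Administer first dose of study drug in clinic after IOP is taken". SAP 9.5.1.3.3 likewise places the Visit 3 IOP "prior to the first q.d. AM dosing".

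On reporting:

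- **BCVA:** "The BCVA will be measured on both eyes in LogMAR at every study visit" (SAP 9.5.1.4.2). SAP 9.7.1.6.2 summarizes change from baseline at every post-baseline visit and counts vision loss by visit.
- **Slit lamp:** it is also done at each visit (SAP 9.5.1.4.3). SAP 9.7.1.6.3 tabulates post-baseline shifts in anterior chamber cells, flare and conjunctival hyperemia.
- **Visit assignment:** "The nominal visits listed in the CRF will be used in the summaries" (SAP 9.7.1, Visit Windows).
- **Adverse events:** clinically significant slit-lamp abnormalities from Visits 3 to 6 are entered as AEs (SAP 9.5.1.4.3; Protocol Appendix 4). SAP 9.7.1.6.1 calls an event treatment-emergent if its start date is the first-dose date or later, up to the last dose.

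**The concern.** A post-baseline row in a safety table is normally read as an on-treatment row. At Visit 3 that reading would be wrong, because the planned exams take place before any exposure. The AE rule has the same gap: it works by date, and the pre-dose exam and the first dose share a date.

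This is a first-in-human study (Protocol 1.2). TEAE frequency heads the list of safety assessments (Protocol 2.2.3), and Protocol 9.4.3 bases the safety assessment partly on TEAEs. Conjunctival hyperemia is the effect the sponsor expects (Protocol 1.3.3) and is one of only three slit-lamp signs with a shift table. A Visit 3 hyperemia shift could be taken for an early drug effect when it cannot be one.

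**Working it through.** The plan gives no figure on this point, so the check sets the rules side by side.

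**Step 1. Are the Visit 3 exams before the dose?** Protocol 7.1.3 presents its order as a suggestion, so it is not enough alone. Other sections give the same sequence:

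| Link | Source |
|---|---|
| BCVA comes before slit lamp and IOP | Protocol Appendix 3: "BCVA testing should precede slit lamp examination, intraocular pressure measurement" |
| Slit lamp comes before IOP | Protocol Appendix 5: "IOP measurement should be conducted after the biomicroscopy exam is completed" |
| 8AM IOP comes before the first dose | Protocol 5.1.2; SAP 9.5.1.3.3; SAP Appendix I, footnote 12: "After 8:00AM IOP measurement" |

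Chained together: BCVA, slit lamp, IOP, first dose. Both exams are pre-dose by plan.

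**Step 2. How does the SAP class them?** Baseline closes at Visit 2 and visits are nominal, so Visit 3 has its own row. The SAP does not define a post-baseline visit, but with baseline ending at Visit 2, Visit 3 is one. SAP 9.7.1.6.2 and 9.7.1.6.3 make no exception for it. The reported Visit 3 change is

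change at Visit 3 = (Visit 3 value) − (Visit 2 value),

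the difference between two untreated measurements a day apart. It holds no drug effect.

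The rows for Visits 4 to 6 are not wrong. They compare on-treatment values with an untreated Visit 2 value.

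**Step 3. Which slit-lamp findings become TEAEs in error?** Apply the date rule to a clinically significant abnormality by its recorded onset:

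| Recorded onset | TEAE under SAP 9.7.1.6.1? | Correct? |
|---|---|---|
| Day 0 or earlier | No | Yes |
| Day 1, before the dose | Yes | No |
| Day 1, after the dose | Yes | Yes |
| After Day 1, up to last dose | Yes | Yes |

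Only the second row is misclassified. The rule in SAP 9.5.1.4.1 that treats conditions present at screening as baseline does not cover a finding new on the morning of Visit 3.

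**Step 4. What does TEAE status control?** In SAP 9.7.1.6.1 it governs the counts of events leading to drug discontinuation or study termination, the matching listing, and the rule that shows a missing severity as severe and a missing relationship as related. The tables by system organ class and preferred term cover all AEs and do not change.

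**Step 5. Is efficacy touched?** No. The IOP baseline is the time-matched Visit 2 value (Protocol 2.2.2 and Section 9), and the Visit 3 IOP is not an efficacy time point.

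**The case against.** The strongest reply has four parts.

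1. **Visit 2 is the protocol's baseline visit.** The SAP follows it, Visit 3 is a separate row, and nothing states that post-baseline means on-treatment. This is fair, and it limits the harm to a likely misreading. It does not remove the gap, because nothing in the tables as planned tells the reader that the Visit 3 row precedes exposure.

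2. **The TEAE route is narrow.** The slit lamp is also done at Visit 2, the day before, and an onset dated then is not treatment-emergent. This stands: only Day 1 onsets before dosing are affected. The missing-severity and missing-relationship rule is more remote still, since both items are required AE data and missing data are queried.

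3. **A date rule is a sensible default.** Transient hyperemia is expected, and a reaction hours after the first dose carries the same date as a pre-dose finding. Counting Day 1 onsets favors capture. This also stands, and is why the date rule should remain the default.

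4. **Dropping Visit 3 could lose real data.** The order is only suggested, and the documents do not show that exam or onset times are recorded. An exam actually done after the dose must not become baseline. This stands and shapes the fix.

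A reader might also infer that a fixed share of the safety output is contaminated, because Visit 3 is one of the four visits the SAP treats as post-baseline. That share counts table rows and says nothing about bias. Nor do the documents support inferring that the error makes the drug look worse than vehicle. All arms follow the same masked schedule, so misclassification should be similar in each.

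**Conclusion.** The point holds as a minor one. Followed as written, the SAP reports drug-free Visit 3 BCVA and slit-lamp results as post-baseline, and classes a clinically significant slit-lamp finding as treatment-emergent when its onset is dated to that pre-dose exam.

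No size can be derived. The documents give no rate of new findings between Visit 2 and the Visit 3 exam, so any count of misclassified TEAEs would be assumed. No treatment comparisons of safety are planned unless otherwise specified (SAP 9.7.1.6), so the consequence is one of description: some added noise, and possibly slightly raised TEAE counts in every arm.

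The conclusion assumes that sites follow the planned order at Visit 3 and that post-baseline means any visit after Visit 2. It does not extend to blood pressure and heart rate, whose timing relative to the Visit 3 dose is not fixed. It does not question the Visit 2 IOP baseline.

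**What to change.** 1. **SAP 9.7.1, General Conventions.** For BCVA and slit lamp only, define baseline as the last measurement before the first dose: the Visit 3 exam when it was done before dosing as planned, otherwise Visit 2. In the tables of 9.7.1.6.2 and 9.7.1.6.3, keep Visit 3 as a row labelled pre-dose, not as a post-baseline visit. A Visit 3 exam known to have followed the dose stays post-baseline.

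2. **SAP 9.7.1.6.1.** Keep the date-based TEAE rule as the default for Day 1 onsets. Add that a slit-lamp finding first recorded at a Visit 3 exam done before the dose is listed as pre-dose and not counted as a TEAE. Later worsening remains eligible as a TEAE.

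The cost is a few sentences and a table label, with no change to visits, efficacy models or sample size. There are two drawbacks. BCVA and slit lamp would have a different safety baseline visit from blood pressure and heart rate. The pre-dose status of each Visit 3 exam would also have to be confirmed from the visit record, because the documents do not show that exam times are captured.
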